Hospitalization: AEs requiring hospitalization should be considered SAEs. Hospitalization for elective surgery or routine clinical procedures that are not the result of AE (e.g., elective surgery for a pre-existing condition that has not worsened) need not be considered AEs or SAEs. If anything untoward is reported during the procedure, that occurrence must be reported as an AE, either 'serious' or 'non-serious' according to the usual criteria.

Assessment for Determining Relationship of AE to Study Drug:

The relatedness of each AE to study drug must be classified based on medical judgement and according to the following categories. The definitions are as follows:

Related: This category applies to AEs that are considered, with a high degree of certainty, to be related to the study drug. An AE may be considered related when it follows a temporal sequence from the administration of study drug, it cannot reasonably be explained by the known characteristics of the subject's clinical state, environment, or toxic factors, or other modes of therapy administered to the subject. An AE may be considered related when it follows a known pattern of response to the study drug, or if the AE reappears upon rechallenge.

Possibly related (**non-serious AEs only**): This category applies to AEs that are considered to have an unlikely connection to study drug, but a relationship cannot be ruled out with certainty.

Unlikely related (**non-serious AEs only**): This category applies to AEs that do not follow a reasonable temporal sequence from the administration of the study drug. The AE may readily have been produced by the subject's clinical state, environmental or toxic factors, or other modes of therapy administered to the subject.

Unrelated: This category applies to AEs that are considered with a high degree of certainty to be due only to extraneous causes (e.g., subject's clinical state, environment, toxic factors, disease under study, etc.) and does not meet the criteria of other categories above.

There are two types of adverse events, Serious Adverse Events (SAE) and Non-Serious Adverse Events (AEs).

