9.3.2 Safety Analyses

Deaths will be listed regardless of onset for the enrolled analysis set.

The frequencies of safety endpoints will be assessed descriptively as the number and percentage of subjects with events/findings separately for the 3 safety analysis sets.

The frequencies of the following safety endpoints will be tabulated on treatment: AEs by intensity (mild, moderate, severe, total); AEs by relationship to study drug (related, possibly related, unlikely related, not related); SAEs; AEs leading to study drug discontinuation; hepatic-related AEs by intensity; hepatic-related AEs leading to study drug discontinuation; clinically significant laboratory test abnormalities; and LFT elevations based on fold changes above ULN, including ALT or AST > 3x ULN concurrent (on the same laboratory test collection date) with total bilirubin > 2x ULN.

The investigators will determine the intensity of AEs and the relationship of AEs to study drug. The investigators' terms will be coded using the latest version of the Medical Dictionary for Regulatory Activities (MedDRA) available at the start of the study. AEs will be tabulated by system organ class and preferred term. In tables by intensity, if a subject has an AE with different intensities over time, then only the greatest intensity will be reported. In tables by relationship to study drug, if a subject has an AE with different relationships over time, then the highest degree of relatedness to study drug will be reported.

Clinically significant laboratory test abnormalities will be identified as grade 3 to 4 laboratory test results graded according to numeric laboratory test criteria in Common Terminology Criteria for Adverse Events (CTCAE) Version 5.0 (2017), if available. Otherwise, if CTCAE grades are not available, then results will be graded according to numeric laboratory test criteria in Division of AIDS (DAIDS) Table for Grading the Severity of Adult and Pediatric Adverse Events Corrected Version 2.1 (2017). If a subject has a laboratory test abnormality with different toxicity grades over time, then only the highest toxicity grade will be reported.

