#### 6.4.1.3 On-DBT AEs

Frequency tables of on-DBT AEs are provided for the DBT safety analysis set by SOC and PT for the following endpoints:

- AEs by worst intensity (secondary objective #7)
- AEs related to study drug by worst intensity
- SAEs (secondary objective #7)
- AEs leading to study drug discontinuation
- Hepatic-related AEs (secondary objective #9)

- Hepatic-related AEs leading to study drug discontinuation (secondary objective #9)
- Potential drug abuse AEs, displayed in alphabetical order by worst intensity and PT without SOC
- Cardiovascular AEs
- Suicidality AEs.

Frequency tables of AEs by SOC and PT display AEs in descending order of zavegepant pooled within SOC and PT, unless otherwise specified.

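### Protocol 8 defines 'Possibly related' as an unlikely connection, so plausible but uncertain non-serious AEs have no well-fitting category and the single related-AE counts are ambiguous

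*Protocol*

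**What the plan says.** Protocol 8, in the part on determining the relationship of an AE to study drug, sets four categories and makes their use mandatory: "The relatedness of each AE to study drug must be classified based on medical judgement and according to the following categories".

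- *Related*: "considered, with a high degree of certainty, to be related to the study drug". Further sentences are more permissive. They admit an event that follows dosing and has no other reasonable explanation, or that returns on rechallenge, and they add: "An AE may be considered related when it follows a known pattern of response to the study drug".
- *Possibly related* (non-serious AEs only): "considered to have an unlikely connection to study drug, but a relationship cannot be ruled out with certainty".
- The third level, *Unlikely related*, is likewise limited to non-serious events and is worded on timing: "This category applies to AEs that do not follow a reasonable temporal sequence from the administration of the study drug". A second sentence says that another cause could readily account for the event.
- *Unrelated*: "considered with a high degree of certainty to be due only to extraneous causes".

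Protocol 9.3.2 plans a tabulation at all four levels, "AEs by relationship to study drug (related, possibly related, unlikely related, not related", and keeps the strongest level when an event's relationship changes over time.

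The current SAP is coarser. The overview in SAP 6.4.1.2 has one row for related AEs. SAP 6.4.1.3 lists "AEs related to study drug by worst intensity", and SAP 6.4.1.4 repeats it for open-label zavegepant. None of these shows the levels. SAP 6.4.1 leaves the definition of a related AE to the Core SAP, which is not among the documents.

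**The concern.** A four-step scale should descend from certain, through plausible, to doubtful, to excluded. Here the second step is worded as doubtful, which is what the label of the third step says, and the plausible step is missing.

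An investigator who goes by the label will use *Possibly related* for plausible events. One who goes by the definition will use it for doubtful events. Both can cite the protocol.

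What is at stake is the meaning of the related-AE counts. If the Core SAP counts *Possibly related* as related, the count takes in events that the protocol defines as unlikely to be connected. If it does not, plausible events filed there by label drop out. The tables as planned do not let a reader see which has happened.

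**Working it through.** The plan states no figure to reproduce; the check is a comparison of texts.

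**Step 1: a test case.** Take nausea recorded as an AE soon after a dose in a subject with chronic migraine. Protocol 3.3 lists nausea among the migraine symptoms, and Protocol 5.2 requires at least 8 migraine days in the 28-day Observation Phase, so such events are foreseeable. The timing fits the drug. The drug is a plausible cause, and so is the disease.

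| Category | What the definition asks | Does the case meet it? |
|---|---|---|
| Related | High certainty; or timing with no other reasonable explanation; or known pattern; or rechallenge | Not certain; the disease is another explanation; fits only if nausea is a known pattern or recurs on rechallenge |
| Possibly related | Unlikely connection that cannot be excluded | Second half fits; first half does not |
| Unlikely related | No reasonable temporal sequence; another cause could readily account for it | Second sentence could fit; first does not |
| Unrelated | High certainty that the cause is only extraneous | No |

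No row fits without setting aside part of a definition.

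**Step 2: how the count can move.** Let *a* be events coded *Related* on any reading, *p* plausible and time-compatible but uncertain events, and *u* events with reasonable timing but an unlikely link. The documents give none of these. For illustration only, assume *a* = 5, *p* = 30, *u* = 40, with one event per subject.

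| Core SAP counts *Possibly related*? | Coding | Related count |
|---|---|---|
| No | *p* in *Possibly related*, by label | *a* = 5 |
| No | *p* raised to *Related* by the permissive sentences | *a* + *p* = 5 + 30 = 35 |
| Yes | label followed: *p* in *Possibly related*, *u* in *Unlikely related* | *a* + *p* = 5 + 30 = 35 |
| Yes | definition followed: *u* in *Possibly related*, *p* moved down | *a* + *u* = 5 + 40 = 45 |
| Yes | mixed: *p* by label, *u* by definition | *a* + *p* + *u* = 5 + 30 + 40 = 75 |

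The last row is a ceiling, since it needs every *p* and every *u* event in the same category. The table shows only that knowing the Core SAP rule narrows the range without closing it.

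**Step 3: which outputs use relatedness.** The related-AE and related-SAE rows in SAP 6.4.1.2 and the related-AE tables in SAP 6.4.1.3 and 6.4.1.4 do. The *Possibly related* wording bears only on non-serious events. Secondary safety endpoints 7 to 9 (Protocol 3.2) cover AEs by intensity, SAEs, discontinuations, laboratory and liver findings and hepatic AEs, and do not use relatedness. Nor do the all-causality AE tables.

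**The case against.** The strongest reply is that the gap is softer in use than on paper. Classification rests on medical judgement as well as on the categories. The permissive sentences under *Related* take in some plausible events. The second half of the *Possibly related* definition points towards its label, and Protocol 9.3.2 lists the levels in an evident order. The two middle categories can also be told apart on timing. All of this stands, and it is why the expected result is inconsistent coding, not events with nowhere to go. It does not close the gap: the temporal-sequence sentence fails whenever the disease is a reasonable alternative, and judgement must be exercised within the categories.

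Three further points stand:

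- The Core SAP may already say which levels count as related. The rule cannot be called missing; it is only out of sight here.
- SAP 2.3 keeps active versus placebo status blinded, though not dose level. Miscoding should therefore be broadly alike for active and placebo at a given dose.
- The study ended in December 2023 for business reasons, and the SAP was then cut back on purpose (SAP 1). Rewording the protocol cannot change classifications already made. A split by level shows how the codes were used but cannot separate plausible from doubtful events within *Possibly related*.

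A reader might infer that the related-AE tables cannot be interpreted at all, or that the comparison with placebo is biased. The documents support neither. The first overlooks judgement and the unseen Core SAP rule, and the second overlooks the blinding.

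**Conclusion.** The definition of *Possibly related* contradicts its label and leaves no well-fitting definition for a plausible but uncertain link. The related-AE counts in SAP 6.4.1.2 to 6.4.1.4 are therefore ambiguous. This is worth correcting, but it does not threaten the trial's main safety conclusions.

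The size cannot be given, because the documents contain no AE frequencies by relationship level; the illustrative counts above are not evidence of magnitude. Exposure is greatest for absolute related-AE rates and for the open-label extension, which has no control group and was planned for about 1200 subjects (Protocol 5.1).

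The conclusion assumes that sites worked from the Protocol 8 text. CRF instructions or training with a different definition, neither of which is in the documents, would lessen it. Which categories are open to SAEs is a separate question.

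**What to change.** 1. For any further use of this text, reword *Possibly related* in Protocol 8 to describe a plausible but not certain relationship, without the reference to an unlikely connection. Check that *Unlikely related* then also takes events with reasonable timing but a more likely cause, which its first sentence now excludes.
2. For the clinical study report, restore the tabulation at the four levels that Protocol 9.3.2 specifies, on double-blind and on open-label treatment. The SAP revision history records that a breakdown by level was dropped from the double-blind related-AE table only in Version 9, so a specification for it has existed.
3. Repeat in SAP 6.4.1 which levels the Core SAP counts as related.
4. Footnote the related-AE tables with the Protocol 8 definition under which the data were collected.

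The cost is a small wording change, one cross-reference, a footnote and one extra table split, using relationship data that the protocol already requires. The split does not recode past events. It lets a reader see how much of each related count rests on the category with the faulty definition.

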8.1 Serious Adverse Events

8.1.1 Definition of Serious Adverse Event (SAE)

An SAE is any event that meets any of the following criteria at any dose:

- Death
- Life-threatening
- Inpatient hospitalization or prolongation of existing hospitalization
- Persistent or significant disability/incapacity
- Congenital anomaly/birth defect in the offspring of a subject who received zavegepant
- Other: Important medical events that may not result in death, be life-threatening, or require hospitalization, may be considered an SAE when, based upon appropriate medical judgment, they may jeopardize the subject and may require medical or surgical intervention to prevent one of the outcomes listed in this definition. Examples of such events are (but not limited to):
 - o Intensive treatment in an emergency room or at home for allergic bronchospasm
 - o Blood dyscrasias or convulsions that do not result in inpatient hospitalization

- o Development of drug dependency or drug abuse
- o Potential drug induced liver injury (see Section 8.4)
- o Abuse or Overdose of medication
 - Potential study drug abuse (including cases of excessive non-compliance with study drug dosing instructions or subjects who discontinue treatment without returning study drug) should be documented in the source record and reported as an AE or SAE as appropriate. Investigators must monitor subjects for possible cases of abuse of study drug (subjects taking study drug for non-therapeutic purposes, e.g., for psychoactive effects such as high or euphoria). Investigators should obtain more information and explanation from subjects when there are study drug accountability discrepancies
 - Potential study drug overdose is defined in Section 8.3

In general, hospitalization signifies that the subject has been detained (usually involving at least an overnight stay) at the hospital or emergency ward for observation and/or treatment that would not have been appropriate in the physician's office or outpatient setting. When in doubt as to whether 'hospitalization' occurred or was necessary, the AE should be considered serious.

The following hospitalizations are not considered SAEs in Biohaven clinical studies (but may be considered non-serious AEs):

- A visit to the emergency room or other hospital department <24 hours that does not result in an admission (unless considered "important medical event" or event that is life threatening);
- Elective surgery planned prior to signing consent;
- Admissions as per protocol for a planned medical/surgical procedure;
- Routine health assessment requiring admission (i.e., routine colonoscopy);
- Admission encountered for another life circumstance that carries no bearing on health and requires no medical intervention (i.e., lack of housing, care-giver respite, family circumstances).

Disability/incapacitating: An AE is incapacitating or disabling if the experience results in a substantial and/or permanent disruption of the subject's ability to carry out normal life functions.

8.1.2 Collection and Reporting Serious Adverse Events

Following the subject's written consent to participate in the study, all SAEs, whether related or not related to study drug, must be collected, including those thought to be associated with protocol-specific procedures. All SAEs must be collected that occur during the Observation

Phase and throughout the course of the study, up to and including the End of Treatment Visit and through the Follow-up Week 8 Visit. The investigator should report any SAE occurring after this time period that is believed to be related to study drug or protocol-specific procedures.

All SAEs should be followed to resolution or stabilization.

An SAE report should be completed for any event where doubt exists regarding its status of seriousness.

If the investigator believes that an SAE is not related to the study drug but is potentially related to the conditions of the study (such as a withdrawal of previous therapy or a complication related to study procedure), the relationship should be specified in the narrative section of the SAE Report Form.

SAEs, whether related or not related to study drug, overdose (see Section 8.3), potential drug induced liver injury (see Section 8.4) and pregnancies (see Section 8.1.3) must be reported within 24 hours of the Investigator becoming aware of the event.

The Investigator is responsible for submitting all applicable events to the Independent Review Board (IRB) as per the IRB's reporting requirements. Additionally, the Investigator, or designated staff, is responsible for entering the SAE information into the Case Report Form (CRF) and/or system (i.e., event term, start/stop dates, causality, and severity).

Any serious adverse event must be reported immediately or no later than 24 hours after awareness of the event to PPD Pharmacovigilance (PVG). A written description of any serious adverse event, using the PPD SAE report form, must be sent to PPD PVG by facsimile (fax), which is the preferred method of submission, within 24 hours after awareness of the event:

• North America Fax – [name]

If a form is unable to be submitted within 24 hours, the SAE may be reported by telephone via the Safety Hotline Number:

• North America Telephone – [name]

If only limited information is initially available, follow-up reports are required. If an ongoing SAE changes in its intensity or relationship to study drug or if new information becomes available, a follow-up SAE report should be sent within 24 hours of the Investigator becoming aware of the updated information using the same procedure used for the transmission of the initial SAE and the same event term should be used.

The minimum information required for an initial SAE report is:

Sender of report (Site number, Investigator name)

Subject identification (subject number)

Protocol number

SAE term (if an SAE is being reported)

8.1.3 Pregnancy

If, following the Baseline Visit, it is subsequently discovered that a study subject is pregnant or may have been pregnant at the time of the investigational product exposure, including during at least 6 half-lives after the product administration, the investigational product will be permanently discontinued in an appropriate manner (i.e., dose tapering if necessary for subject safety). Protocol-required procedures for study discontinuation and follow-up must be performed on the subject unless contraindicated by the pregnancy (i.e., x-ray studies). Other appropriate pregnancy follow-up procedures should be considered if indicated.

Sites should instruct patients to contact the Investigator if they become pregnant during the course of the study. The investigator must immediately notify the Biohaven (or designee) Medical Monitor and PPD of the event and complete the Pregnancy Form in accordance with SAE reporting procedures as described in Section 8.1.2. The pregnancy should be reported using paper forms, which should be faxed to PPD PVG by facsimile (fax), which is the preferred method of submission, within 24 hours after Investigator/site awareness of the event:

- North America [contact]
- Or if the form cannot be faxed or emailed ([contact]; subject line must include "Biohaven Protocol BHV3500-302"), reported via phone to the PPD Safety Hotline at North America: [name] or EU EMEA: [contact].
- Once the paper form is available, the data must be reported per standard procedures.

Follow-up information regarding the course of the pregnancy, including perinatal and neonatal outcome and, where applicable offspring information must also be reported on a Pregnancy Report Form.

Any pregnancy that occurs in a female partner of a male study participant should be reported to the sponsor/PPD. Information on this pregnancy will be collected on the Pregnancy Report Form, as appropriate.

8.2 Non-Serious Adverse Events

A *non-serious adverse event* is an AE not classified as serious.

8.2.1 Collection and Reporting of Non-serious Adverse Events

Non-serious AE information should be collected from the start of the Observation Phase intended to establish a baseline status for a subject and should be captured through the Follow-up Week 2 Visit except for non-serious suicidality AEs which should be captured through the Follow-up Week 8 Visit (see Section 6.2.5).

Non-serious adverse events should be followed until conclusion or stabilization or reported as SAEs if they become serious. Follow-up is also required for non-serious AEs that cause interruption or discontinuation of study drug or those that are present at the end of study treatment.

8.2.2 Laboratory Test Abnormalities

The following laboratory test abnormalities should be captured on the non-serious AE CRF page or SAE Report Form (paper or electronic) as appropriate:

- 1. Any laboratory test result that is clinically significant or meets the definition of an SAE;
- 2. Any laboratory abnormality that required the subject to have the study drug discontinued or interrupted;
- 3. Any laboratory abnormality that required the subject to receive specific corrective therapy.

8.3 Overdose

An overdose is defined as the accidental or intentional administration of any dose of a product that is considered both **excessive** and **medically important**.

All occurrences of medically significant overdose (suspected or confirmed and irrespective of whether it involved study drug) must be communicated to Biohaven or a specified designee within 24 hours and be fully documented as an SAE. Details of any signs or symptoms and their management should be recorded including details of any treatments administered.

Asymptomatic dosing errors (e.g., accidentally taking more than 4 capsules instead of prescribed dose of 4 capsules in one calendar day) should be reported as deviations.

8.4 Potential Drug Induced Liver Injury (DILI)

Wherever possible, timely confirmation of the initial liver-related laboratory abnormalities should occur prior to the reporting of a potential DILI event. All occurrences of potential DILIs, meeting the defined criteria, must be reported as SAEs as per Section 8.1.2.

Potential drug induced liver injury is defined as:

1. ALT or AST elevation > 3x ULN

AND

2. Total bilirubin > 2x ULN, without initial findings of cholestasis (elevated serum alkaline phosphatase)

AND

3. No other immediately apparent possible causes of ALT or AST elevation and hyperbilirubinemia, including but not limited to, viral hepatitis, pre-existing chronic or acute liver disease, or the administration of other drug(s) known to be hepatotoxic.

If any potential DILI is identified and meets the criteria above, the Biohaven Medical Monitor (or designee) should immediately be contacted for further instruction and whether the subject must discontinue from the trial and appropriate follow-up requirements.

8.5 **Adverse Events of Special Interest**

Not applicable.

